CASTomize Pilot Study Protocol

Principle investigator: [name]

Co-investigator: [name], [name]

Industrial collaborator: [name], [name], [name]

CASTomize pilot study protocol: a randomized controlled trial comparing CASTomize 4D printed cast versus standard of care fiberglass cast on fracture reduction and patient reported outcomes.

Abstract

Background: For many years, traditional fibreglass casting has been the gold standard of immobilisation for distal radius fractures (DRFs). However, the traditional method of casting has obvious disadvantages such as poor patient comfort, inability to be in contact with water, difficulty observing skin underneath and requiring multiple cast changes in the patients care journey. This study compares the Castomize 4D printed casts versus the conventional fiberglass cast in fracture immobilisation, and various patient reported outcomes.

Methods/design: This study is a randomised control trial comparing Castomize 4D printed cast versus conventional fibreglass casts in isolated conservatively treated distal radius fractures. The primary outcome measure is fracture reduction. Secondary outcome measures include patient reported outcome measures such as the Adult Rated Cast Evaluation Questionnaire (ARCEQ)[1][2], comfort of the cast, quality of life assessed with the EQ-5D-5L questionnaire[3], cost-effectiveness and adverse events occurrence. In total, 30 patients will be included and followed for 6 months.

Trial registration: Pending

Registration number: Pending

Background

Displaced distal radius fractures (DRF) are very common in the adult population and their incidence is still on rising trend due to aging population. This is an issue which is pervasive across all ages, but most common in the elderly. In 2019, 180 million fractures happened worldwide. An average of 5 fracture incidents occurs every second. The current gold standard in fracture immobilisation is via the application of a fibreglass cast. However, the current fibreglass cast has multiple disadvantages. The cast is bulky, has poor ventilation and cannot come into contact with water. This gives patients considerable discomfort, and are unable to bathe and provide hygiene to their injured limb for the duration of the casting. Because the cast is not breathable, skin maceration, itchiness and wounds

may become an issue. In this light, multiple casts changes become necessary to reduce the risk of soft tissue complications and to provide patient comfort. This increases the wastage of materials for the fibreglass casting as well as increases healthcare burden for the cast changes.

Castomize has created a 4D printed cast with its proprietary materials and designs aimed at overcoming the challenges in the traditional casting methods. Its 4D printed casts are lightweight and breathable, allowing contact with water and hygiene. Its design facilitates visualisation of the skin and soft tissue conditions. It is also remouldable, potentially only requiring one device for the duration of the patients care journey.

The design of the 4D printed cast was done in collaboration with orthopaedic clinicians, prosthetists and senior casting technicians optimised for clinical use. A biomechanical test was performed to evaluate the biomechanical properties of the 4D printed cast in comparison to the conventional fibreglass casts and were found to be less stiff and with a lower load to failure. This was however accessed to be not clinically significant.

Therefore, this study aims to compares the Castomize 4D printed casts versus the conventional fiberglass cast in fracture immobilisation and various patient reported outcomes.

Methods/design

This manuscript is written according to the Consolidated Standards for Reporting Trials (CONSORT statement) and Standard Protocol Items: Recommendations for Interventional Trials (SPIRIT guidelines).

Objectives

The primary aim of the study is to assess non inferiority of the Castomize 4D printed cast versus conventional fibreglass casts in fracture immobilisation and reduction.

The secondary aim of the study is to assess differences in patient reported outcomes measures (ARCEQ, comfort of the cast, EQ-5D-5L, cost-effectiveness and adverse events occurrence) in the Castomize 4D printed cast versus conventional fibreglass casts.

Design, participants, interventions and outcomes

Study design and randomization

A randomised controlled trial will be conducted in a single institution: TTSRH.

Patients will be recruited at the outpatient clinic. Patients who meet the inclusion and exclusion criteria will be recruited and randomised into 2 groups. Randomisation will be carried out via block randomisation via a computer generated randomization sequence.

Group 1: Castomize 4D printed cast (Figure 2)

Patients randomized to group 1 will undergo fracture immobilisation with the Castomize 4D printed cast via the care team (Casting technician/ clinical team). The Castomize 4D printed cast is appropriately heated and then moulded to the patients wrist as per usual manipulation and reduction techniques. The cast is held in position until hardened.

Group 2: Conventional casting (Figure 1)

Patients randomized to group 2 undergo fibreglass casting as per the standard of care.

In both groups, post casting X-rays are taken to assure fracture reduction and recasting may be attempted in the event of inadequate fracture reduction.

A patient information sheet will be provided to the patient explaining the study protocol, and what to look out for in caring for their casts.

Inclusion criteria

- Age \geq 21 years
- Distal radius fracture for conservative treatment within 3 weeks of initial injury

Exclusion criteria

- Concomitant injuries to the ipsilateral extremity, interfering with the treatment of the DRF (Example: concomitant elbow fracture that requires further immobilisation with a above elbow cast)
- Inability to complete study forms due to any cognitive, mental issues.
- Pregnant women

Study procedures and timeline

Measurements will take place at 6 time points as shown in Table 1. These time points are baseline (T0), 1 week (T1), 2 weeks (T2), 6 weeks (T3), 3 months (T4) and 6 months (T5) after inclusion in the study. At T0, baseline characteristics will be gathered. An inclusion form will be filled in by the treating physician providing fracture and treatment-specific information. Second, patients receive a questionnaire, providing predominantly patient and injury-specific information. The list of baseline characteristics is shown in Table 2. Patients receive questionnaires at T1 to T5. These questionnaires are carried out by phone call. Posterior-anterior (PA) and lateral radiographs of the wrist will be taken at T0 (before and after reduction) and during follow-up at T1 –T4 as per standard of care. Physical examination of the wrist will take place at T4 and will be performed by the research team. Study visit may be administered via phone call. Functional tests will be performed at patient earliest appointment.

Table 1 Schedule of activities

	T0 Baseline	T1 D7 \pm 3	T2 D14 \pm 3	T3 D35 \pm 7	T4 D84 \pm 14	T5 D168 \pm 21
Inclusion form	✓					
X-rays*	✓	✓	✓	✓	✓	
Functional tests**					✓	✓
VAS		✓	✓	✓	✓	✓
Photograph		✓				
Comfort of cast		✓	✓	✓		
Analgesic use		✓	✓	✓	✓	✓
EQ 5D5L		✓***		✓	✓	✓
ARCEQ				✓	✓	✓
MCQ- iMTA				✓	✓	✓

PCQ- iMTA				✓	✓	✓
-----------	--	--	--	---	---	---

*X-rays before and after reduction (obtained from standard of care results if available)

**ROM, grip strength done by study team. ROM, DRUJ and Kapandji will be collected as part of standard of care if available

*** EQ 5D5L status pre-fracture and post-fracture sustainment

Table 2 Baseline characteristics

Baseline characteristics	
Date of emergency room visit	Sex
Affected wrist	Date of Birth
Method of reduction	
	Hand dominance
	Mechanisms of injury
	Smoking Status
	General medical history
	Previous injuries of the affected extremity
	La Fontaine criteria

Outcome

Primary outcome The primary outcome of this study is the occurrence of fracture displacement assessed on PA and lateral radiographs at 1, 2 and 6 weeks. Displacement of the radius is defined by: As compared to the post reduction radiograph at T0, Displacement of : > 15° of dorsal angulation, > 20° of volar angulation, < 15° of radial inclination, > 3mm of radial shortening and > 2mm intraarticular step-off or gap. Measurements will be on standard PA and lateral radiographs of the wrist by trained members of the research team.

Secondary outcomes An overview of measurements is shown in Table 1.

- Comfort of the cast assessed via pictorial representation of pressure marks or areas of discomfort.
- Severity of pain evaluated with the Visual analogue Score (VAS)
- Patient will describe their average wrist symptoms over the past week on a scale of 0-10 using Adult Rated Cast Evaluation Questionnaire (ARCEQ) [6][7].
- Quality of life will be assessed using the 5-level EuroQol (EQ-5D-5L) scoring questionnaire.
- Cost-effectiveness will be measured using the Medical Consumption Questionnaire (iMCQ) and the Production Consumption Questionnaire (iPCQ) [8].
- Physical examination:
 - Range of motion (ROM) of the wrist will be measured with a goniometer. ROM concerns dorsal flexion, volar flexion, radial deviation, ulnar deviation, pronation and supination.
 - Grip strength will be measured with a Jamar hydraulic hand dynamometer. The maximum score for each side over 3 attempts will be used
 - Specific testing of the wrist and hand will be performed namely:
 - distal radioulnar joint (DRUJ) stability tested with the DRUJ ballottement test

- opposition of the thumb using the Kapandji score
- finger stiffness will be measured with finger-to-palm distance, tested from the tip of the finger to the distal palmar crease when the fingers are in maximal active flexion

ROM and grip strength on the injured side will be compared with the uninjured side.

- Number of conversions to surgical treatment and other (serious) adverse events will be monitored. (Eg: Skin complications)

It is expected that a proportion of patients will fail conservative treatment with displacement of the distal radius fracture at week 1 or week 2 follow up. These patients will continue with surgical fixation of their fractures and no further trial procedures will be required.

Adverse events reporting

All adverse events reported by the patient or observed by the treating physician or researcher will be recorded. Serious adverse events (SAE) will be reported to the Domain Specific Review Board (DSRB), which approved the protocol.

Serious adverse events are defined as:

- Skin related problems requiring surgical intervention (Eg: Ulcer, infection, necrosis)
- Compartment syndrome
 - Cast related injury to the patient resulting in loss of limb or life

Study related serious adverse events are defined as:

- Compartment syndrome

Fig 1 Conventional Fiberglass cast[9]

Fig 2 CASTomize 4D printed cast

Data analysis

General descriptive statistics will be performed on baseline patient and fracture characteristics. Patients will be analysed according to the intention-to-treat principle.

Primary outcome

The primary outcome, fracture re-displacement, will be analysed using a mixed-effects logistic regression. To account for clustering, a random intercept for the hospitals will be used. Fixed effects will be the covariates we adjust for as reported in the literature, namely age, presence of osteoporosis, and fracture characteristics. If new prognostic factors will be identified and reported in the literature, these factors will also be added as covariates.

Secondary outcomes

For secondary outcomes, trends between baseline and follow-up time points (T0-T5) will be assessed using linear mixed models for repeated measures. This accounts for comfort of the cast, recovery of function and grip strength, pain severity (VAS), ARCEQ and EQ-5D-5L scores. The number of conversions to surgical fixation and complications will be determined using Fisher Exact or Chi-square test, depending on the magnitude of results.

Cost-effectiveness analysis

Both cost-effectiveness (CEA) and cost-utility (CUA) analysis will be performed from a societal perspective. For the calculation of medical costs, we will use charges as published in Singapore guidelines as a proxy of real costs. The unit per price of the cast application in patients with DRF will be calculated with the microcosting method. Intramural costs (i.a. additional diagnostics, number of hospital visits, in case of hospital admission the length of stay etc.) are collected from the electronic health record. Productivity costs will be registered in detail by the iPCQ. The iMCQ and the iPCQ are validated by the Institute of Medical Technology Assessment (Erasmus University, Rotterdam, The Netherlands).

The difference in costs and effects of CASTomize instead of a circumferential cast will be calculated as incremental cost-effectiveness ratio (ICER). The primary effect outcome measures will be the number of re-displacements for the CEA and quality-adjusted life years (QALY) for the CUA. QALYs will be measured, based on the Singaporean tariff for the EQ-5D-5L.

The sensitivity analysis will assess the robustness of the results to changes in costs and effect parameters. Bootstrapping with 1000 replications will be used to estimate 95% confidence intervals around cost differences and the uncertainty surrounding the ICERs. This will be graphically presented on cost-effectiveness planes and acceptability curves using the net benefit framework. For the time horizon of 6 months, discounting is not necessary.

Data management

All data are handled confidentially and anonymized in compliance with the Singapore Personal Data Protection Act (PDPA). Personal data of participants will be changed by a study number. This number is used for all study documentation, study reports and publications. The key of this study number will be handled by an independent researcher. During the study period, all data will be collected and managed using GemsTracker electronic data capture tools. Paper case report forms are entered in GemsTracker by the researcher and the original paper case forms will be filed in the investigator site file at the recruiting hospital. All data is stored for 10 years.

Data monitoring

Since the study is labelled as low risk, a data safety monitoring board is not required.

References

- [1] M. Neubauer, "DASH Score," *Heartbeat Medical*, Jul. 22, 2021. <https://heartbeat-med.com/resources/dash-score/> (accessed Nov. 06, 2022).

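### The title, abstract and primary aim claim fracture reduction, but the primary outcome measures loss of reduction after T0, so it does not support a non-inferiority claim on reduction

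*Combined protocol and SAP*

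**What the plan says.** The title compares the casts on fracture reduction, and the abstract says "The primary outcome measure is fracture reduction". Under Objectives, the primary aim is to "assess non inferiority of the Castomize 4D printed cast versus conventional fibreglass casts in fracture immobilisation and reduction".

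The Outcome section defines something else: "The primary outcome of this study is the occurrence of fracture displacement assessed on PA and lateral radiographs at 1, 2 and 6 weeks". The definition begins "As compared to the post reduction radiograph at T0" and then lists five thresholds: dorsal angulation, volar angulation, radial inclination, radial shortening and intra-articular step-off or gap. The Data analysis section uses a third name: "The primary outcome, fracture re-displacement, will be analysed using a mixed-effects logistic regression". The cost-effectiveness section also counts re-displacements.

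Under Study design and randomization, the 4D printed cast is heated and moulded while the wrist is being manipulated and reduced. In both groups X-rays follow casting, and "recasting may be attempted in the event of inadequate fracture reduction". The plan gives no criterion for inadequate reduction and no limit on attempts, and it does not ask for attempts to be counted. The listed secondary outcomes include neither alignment at T0 nor recasts.

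**The concern.** Obtaining a reduction and keeping it are two outcomes. The aim claims both, while the endpoint starts from the film that follows reduction and looks forward. Patients are randomised to a cast, and the new cast is shaped during the reduction, so alignment on a post-casting film may itself depend on the arm. An endpoint that takes this film as its starting point can remove part of the effect that the aim names.

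What is at stake is the conclusion. If the new cast needed more attempts, or left more residual deformity that then stayed stable, the trial could still report non-inferiority in reduction. That is half of the primary aim.

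**Working it through.** No figure in the plan bears on this point. The 30 patients are given without a derivation, and the argument does not depend on that number. The check is a comparison of passages, followed by an illustration.

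**1. Which events can enter the primary outcome?** Films that count are those at weeks 1, 2 and 6.

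- *First reduction inadequate, corrected by recasting at T0.* This happens before the first counted film, and follow-up starts from the corrected position. It is not an event, whether the thresholds are changes or absolute values.
- *Residual deformity accepted at T0, stable afterwards.* It is not an event under a change threshold. It is an event under an absolute threshold if the residual value is already beyond the limit.
- *Good reduction, later lost.* It is an event if the movement is large enough. This is what the endpoint is built to count.

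**2. Are the thresholds changes or absolute values?** The opening words of the definition point to change. One item, "< 15° of radial inclination", makes sense only as an absolute value: a change of less than 15° would count a stable wrist as displaced. The other four can be read either way.

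**3. Which film is the reference after a recast?** It is not stated. Let the angle be *a1* on the first post-cast film, *a2* after a recast and *a3* at follow-up. The change is *a3 − a1* or *a3 − a2*, and the two differ by *a1 − a2*, the correction gained by recasting. The same wrist can be an event under one choice and not under the other. Entry up to 3 weeks after injury also leaves open that the post-reduction film predates the study cast.

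**4. How much does the reading matter?** Illustration for the dorsal criterion (15°). The assumptions are not from the documents: residual angle after reduction normal with mean *m* and SD 5°; drift in the cast normal with mean *d* and SD 7°, independent of the residual angle and equal in both arms.

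- Change reading: P = 1 − Φ((15 − d)/7), which does not contain *m*.
- Absolute reading: P = 1 − Φ((15 − m − d)/√(5² + 7²)), with √74 = 8.60.

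| Mean drift *d* | Change, any *m* | Absolute, *m* = 0° | Absolute, *m* = 8° | Absolute: difference |
|---|---|---|---|---|
| 3° | 4.3% | 8.2% | 32.1% | 23.9 points |
| 6° | 9.9% | 14.8% | 45.4% | 30.6 points |
| 9° | 19.6% | 24.3% | 59.2% | 34.9 points |

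Under the change reading, an arm with 8° more residual angulation has the same event rate. Under the absolute reading, the difference shows, but it is mixed with later drift and cannot be separated from it.

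**5. Is reduction picked up elsewhere?** Conversion to surgery is a listed secondary outcome, and the cost data (visits, diagnostics, cast application) would absorb some of the burden of recasting. Both are indirect. Neither gives achieved alignment or first-attempt success by arm.

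**The case against.** The strongest reply is that reduction is shorthand for maintaining reduction. The operative text is consistent on this: the outcome definition, the primary analysis and the cost-effectiveness measure all concern displacement after reduction, and the background states the comparison as immobilisation without mentioning reduction. Eligibility does not require a fracture that needed reducing. That may well be the intention, but it supports correcting the aim and abstract. It does not support leaving a non-inferiority claim on reduction in place.

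A reader might also infer something stronger: that recasting resets the reference and that poorer reduction with the new cast therefore cannot show in the endpoint at all. The documents do not support this. The radial-inclination threshold reads as absolute, and if the others are absolute too, residual malreduction partly enters the endpoint. That the reference film follows any recast is a reasonable inference, but it is not stated. Poor reduction that leads to surgery would also appear among the conversions.

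Nor should recasts be equated with failure to achieve reduction. If recasts succeed, the arms differ in first-attempt success, not in the reduction finally achieved.

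Finally, the added table is not free of difficulty. The note to Table 1 makes X-rays depend on what standard of care provides, and the plan does not define an adequate reduction. Both points stand and shape the fix.

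**Conclusion.** The point holds in a limited form. The outcome claimed in the title, abstract and primary aim is not the one defined and analysed. Two gaps follow, of different certainty. A failed first reduction corrected by recasting at T0 is uncounted under every reading. Poorer residual alignment is missed only to the extent that the thresholds are changes from T0, and the plan leaves that open for all but radial inclination.

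The size cannot be taken from the documents. The range in the illustration (no effect on the event rate under the change reading, about 24 to 35 points under the absolute reading for 8° of residual angulation) rests on assumed distributions. It shows only how much depends on the missing definition. Under either reading, the endpoint does not support a claim of non-inferiority in reduction. A claim limited to loss of reduction in the cast would match what is measured. The change should be made before the trial's conclusions are drawn.

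**What to change.** 1. Name the primary outcome and the primary aim as loss of reduction (re-displacement) in the cast, in the title, abstract, Objectives, Outcome and Data analysis, and limit the non-inferiority claim to it.
2. State which T0 film is the reference when a recast occurs, and for each of the five thresholds whether it is a change from that film or an absolute value.
3. Add a descriptive secondary outcome by arm: radiographic alignment on the first post-cast film, using the same parameters as the primary outcome, and the number of casting attempts. Reporting measured values avoids the need for a new cut-off for adequate reduction. Report the number of missing films by arm.

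The cost is wording, some extra measurement of existing films, and a count from treatment records. The downsides are a narrower primary claim and possible gaps where standard of care supplied no post-casting film. No clinical rule changes.

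### The primary aim is non-inferiority, but the plan has no margin, alpha, confidence-limit rule or basis for 30 patients, and 30 patients cannot reliably support that conclusion at margins below about 25-30 points

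*Combined protocol and SAP*

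**What the plan says.** The Objectives section sets the hypothesis type: "The primary aim of the study is to assess non inferiority of the Castomize 4D printed cast versus conventional fibreglass casts". The title labels the trial a pilot: "CASTomize pilot study protocol: a randomized controlled trial comparing CASTomize 4D printed cast versus standard of care fiberglass cast". The Abstract gives the size: "In total, 30 patients will be included and followed for 6 months". No sample-size section follows.

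Under Outcome, the primary endpoint is "the occurrence of fracture displacement assessed on PA and lateral radiographs at 1, 2 and 6 weeks". The angle and millimetre thresholds listed there define displacement in one patient. They are not a margin between arms.

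Under Data analysis: "Patients will be analysed according to the intention-to-treat principle". Then: "The primary outcome, fracture re-displacement, will be analysed using a mixed-effects logistic regression". The next sentence adds: "To account for clustering, a random intercept for the hospitals will be used". The fixed effects listed are age, osteoporosis and fracture characteristics; treatment arm is not named. The section on study design and randomization says: "A randomised controlled trial will be conducted in a single institution".

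The only confidence interval in the document is the bootstrapped one for costs and cost-effectiveness ratios.

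**The concern.** A non-inferiority question is answered by comparing a confidence limit for the treatment difference with a margin fixed in advance. Here the margin, its scale, the confidence level and the comparison rule are all absent, so no result could be declared to meet or miss the primary aim. The planned model reports an odds ratio, while no scale for a margin has been chosen.

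The question has substance: the Background reports that the new cast was less stiff and failed at a lower load in bench testing, although this was judged not clinically significant. If the analysis ended with a non-significant comparison in 30 patients, nothing in the plan would stop that being presented as non-inferiority.

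**Working it through.** **1. The plan's own figure.** The 30 can be neither reproduced nor refuted, because no margin, alpha, power, displacement risk or loss rate is given.

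**2. Inputs.** From the protocol: 30 patients, two groups, a binary primary outcome. Assumed, because the protocol is silent: 1:1 allocation (15 per arm), one outcome per patient, no losses, equal true risks p of 10-40% (2-5% as a check), and 80% power as the meaning of reliable.

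**3. Method.** For risk difference d = p1 − p2 (Castomize minus fibreglass), the Newcombe upper limit is d + √[(u1 − p1)² + (p2 − l2)²], where l and u are each arm's Wilson limits. Non-inferiority is met if this limit lies below the margin. Chances are sums of exact binomial probabilities over all pairs of counts.

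**4. Identical observed counts.** With 0/15 in both arms the Wilson upper limit is z²/(15 + z²). At z = 1.96 this is 3.84/18.84 = 20.4 points; at z = 1.645 it is 2.71/17.71 = 15.3 points. With 3/15 in both arms at z = 1.96, the Wilson limits are 0.070 and 0.452, so the upper limit is √(0.252² + 0.130²) = 28.3 points.

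| Displaced in each arm | 0 | 1 | 2 | 3 | 4 | 5 | 6 | 7 |
|---|---|---|---|---|---|---|---|---|
| Upper limit, two-sided 95% (points) | 20.4 | 23.8 | 26.4 | 28.3 | 29.8 | 30.9 | 31.5 | 31.9 |
| Upper limit, one-sided 0.05 (points) | 15.3 | 19.1 | 21.9 | 23.9 | 25.5 | 26.6 | 27.3 | 27.6 |

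**5. Operating characteristics when the casts are truly equal.**

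| True risk in both arms | 10% | 20% | 30% | 40% |
|---|---|---|---|---|
| Two-sided 95%: chance of meeting 20 points | 34% | 28% | 27% | 25% |
| Two-sided 95%: chance of meeting 30 points | 70% | 58% | 51% | 45% |
| Two-sided 95%: smallest margin with 80% power (points) | 34 | 40 | 42 | 43 |
| One-sided 0.05: chance of meeting 20 points | 54% | 42% | 38% | 32% |
| One-sided 0.05: chance of meeting 30 points | 82% | 68% | 60% | 58% |
| One-sided 0.05: smallest margin with 80% power (points) | 29 | 36 | 38 | 39 |
| Average 95% half-width (points) | 25 | 28 | 30 | 31 |

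At risks of 2-5% the smallest margin is about 30 points (two-sided 95%) or 25 points (one-sided 0.05). The distribution moves in steps here: at 2% risk and one-sided 0.05, a 20-point margin falls only just short, at 79.8%.

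**6. Cross-check by normal approximation.** Margin = (1.645 + 0.842)·√(2p(1 − p)/15) gives 27, 36, 42 and 44 points at risks of 10, 20, 30 and 40%, close to the exact one-sided 0.05 row except at 40%, where it is more demanding.

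**7. The logistic model.** Expected events are 30p, that is 3, 6, 9 and 12. The chance that at least one arm has no events is 1 − [1 − (1 − p)^15]². At 10% this is 1 − (1 − 0.206)² = 37%; it is 7% at 20%, and 1% or less at 30-40%. With no events in one arm the maximum-likelihood odds ratio is not finite. With one hospital there is no between-hospital variation from which to estimate the random intercept.

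**8. Illustration only.** If the true risks were 40% and 20%, the two-sided 95% interval would include zero in about 77% of trials.

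**The case against.** The strongest reply is that this is a pilot, that the aim is only to assess non-inferiority, and that the Abstract does not mention it. This explains a small trial and favours rewording over enlarging it. It does not remove the defect: non-inferiority is the stated primary aim, no feasibility or precision objective is given, and without a margin it cannot be assessed either.

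A second reply is that the displacement risk, allocation and alpha are assumed. That stands for every figure in the working, but not for the omissions, which need no assumption. The displacement criteria are joined by the word and, so a literal reading could make events rarer than 10%; the 2-5% check covers this.

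Three stronger readings are tempting, and the documents do not support them.

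- A reader might infer that identical counts can never meet a 20-point margin. That is so only at two-sided 95%. At one-sided 0.05, 0/15 or 1/15 in each arm would meet it, and the plan sets no alpha.
- A reader might infer that the trial would probably miss any margin. At 30 points the chance of success is 45-70% (two-sided 95%) or 58-82% (one-sided 0.05): not dependable, but not unlikely throughout.
- A reader might infer that the sponsor intends to read a non-significant result as non-inferiority. The protocol does not say how such a result would be read; the 77% figure shows a possible misuse, not a planned one.

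The hospital intercept and the unnamed treatment arm are faults in their own right. They add nothing to the argument about size.

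**Conclusion.** The concern holds and needs correction before analysis. Followed as written, the plan has no rule by which its primary aim could be answered; this rests on the text alone. Adding a margin would not by itself be enough. With 15 complete patients per arm, 30 patients cannot reliably support non-inferiority at margins below about 25-30 points, and at risks of 10-40% the margin would have to be 29-43 points, depending on the risk and the alpha. These sizes rest on 1:1 allocation, one outcome per patient, no losses, equal true risks, Newcombe limits and 80% power. Losses would make them worse. It does not follow that 30 is too few for a pilot with an estimation aim.

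**What to change.** Keep 30 patients and restate the primary aim along these lines: to estimate the difference in re-displacement risk (Castomize minus fibreglass) with a 95% confidence interval, to inform the margin and size of a definitive trial; no non-inferiority conclusion will be drawn, and a non-significant difference will not be read as non-inferiority.

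In Data analysis:

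- Report an intention-to-treat risk difference that counts each patient once, as displaced on any week 1, 2 or 6 film, with a small-sample interval such as Newcombe's. Other small-sample methods would serve; what matters is naming one in advance.
- State the expected half-width: about 25-31 points at risks of 10-40% with 15 complete patients per arm, and wider if films are missing. Say how a patient with a missing film is handled, since films come from standard care where available.
- Remove the hospital random intercept, name treatment arm in the logistic model, and keep that model as supportive only, given 3-12 expected events.

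This adds no patients, visits or X-rays. The sponsor gives up a non-inferiority claim that the design could not support, and the unadjusted estimate does not correct for chance imbalance in age, osteoporosis or fracture type.

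If a non-inferiority claim is wanted, the alternative is to justify a margin and resize. By normal approximation, N = 2 × (1.96 + 0.842)² × 2p(1 − p)/margin², with each arm rounded up. For 80% power at one-sided 0.025 and risks of 10, 20 and 30%, a 20-point margin needs 72, 126 and 166 patients in total, and a 10-point margin needs 284, 504 and 660.
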